**Figure 2: LATITUDE NXT 5.0 System**

The primary means of device data collection for the PREEMPT-HF study is through the LATITUDE patient management system. Therefore, LATITUDE enrollment is required for subject participation in the study, and data transmission via LATITUDE (i.e., referred to as “monitored on LATITUDE”) must be confirmed at the baseline visit. During the course of the study if the subject is away from the communicator, sensor data storage to PG memory will continue; however, the next data upload will not occur until the subject is within range of the communicator. To ensure timely data transmission, LATITUDE must be programmed for scheduled follow-ups to occur every 3 months or sooner. At the final study visit, the investigational site must interrogate the subject’s device using the PRM. This will trigger a remote data upload to LATITUDE when the subject returns within range of the communicator.

For the PREEMPT-HF study, Heart Failure Sensors must be turned ON. This must be done via the PRM. The Heart Failure Sensors consists of heart sounds (S3 and S3/S1), respiration (respiratory rate and rapid shallow breathing index), impedance, heart rate and activity.

Only subjects with Heart Failure Sensors turned On, Respiratory Sensor turned ON, and HeartLogic disabled are eligible to participate in the study. The state where HeartLogic is **not** enabled on LATITUDE is referred to as HeartLogic disabled. In this state, the device will continue to collect sensor data, but the HeartLogic Index and Heart Sounds sensor trends will not be displayed on the LATITUDE system, and clinicians will not receive HeartLogic alerts. Sensor data will be stored in the PG for 365 days after which the earliest data are overwritten. The subject must be withdrawn from the study if Heart Failure Sensors will be turned OFF, or if HeartLogic will be enabled. Subjects may remain in the study if the Respiratory Sensor or Sleep Incline Sensor are turned OFF; however, this will be considered as a protocol deviation. The Sleep Incline Sensor measures the subject’s average elevation angle over the programmed sleep schedule. Sleep schedule can be programmed using the PRM.

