**Table 6-1: Visit and Review Schedule**

Visit	Window
Enrollment Visit	The subject may be enrolled at any time following device implant
Baseline Visit	The baseline visit must be conducted at least 7 days following implant, and within 30 days of subject consent
Interim Medical Record Review (6 month)	150 to 210 days from baseline visit
Final Clinic Visit (12 month)	350 to 430 days from baseline visit (or at the point of withdrawal)

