**Table 9-1 Data Collection Schedule**

Procedure/ Assessment	Enrollment Visit	Baseline Visit (Day 0)	Interim Medical Record Review  (150-210 days)	Final Clinic Visit  (350-430 days)
Informed Consent Process, including Signature and Date	X	--	--	--
Inclusion/Exclusion Criteria Assessed	X	--	--	--
Confirmation LATITUDE Transmission	--	X	--	X
Device Information	--	X	X (changes only)	X (changes only)
Distribute Subject ID Card with Site Contact Information	--	X	--	--
Sleep Incline Calibration	--	X	--	--
Demographics	--	X	--	--
Physical Assessment	--	X	--	X
Medical History	--	X	--	--
Blood Labs	--	O	--	O
Cardiac Medications Reviewed	--	X	--	--
Assessment of Adverse Events and Reviewable Clinical Events	--	X	X	X
Supplementary Diagnostics Data Collection	--	--	O	O

 The interim medical record review does not require an in-clinic visit.

\*Please complete the final clinic visit form for subjects withdrawn prior to 350 days

An "X" indicates a mandatory data requirement. Failure to complete will result in a protocol deviation.

An "O" indicates optional but recommended data.

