## 9.2 Device Interrogation / Collection of Programming Data

The device must be interrogated with a PRM at enrollment, baseline and during the final clinic visit. These interrogations are required to confirm the appropriate programming of the device, including Heart Failure Sensors ON, Sleep Incline Sensor ON, and Respiratory Sensor ON. All other device settings can be programmed per clinician discretion. The PRM must also be used to calibrate the Sleep Incline Sensor.

HF Sensor data and Sleep Incline data will be collected via the LATITUDE patient communicator.

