### **9.8 Interim Medical Record Review [150-210 days]**

The interim medical record review must be conducted 150 to 210 days following the baseline visit. It is encouraged to perform the interim medical record review at the time of an in-clinic standard of care visit. If this review coincides with an in-clinic visit, the subject must be asked whether he or she had any reviewable clinical events (RCEs) since the baseline visit. As defined in section 5.1, an RCE is defined as either an all-cause hospitalization, or HF outpatient visit. If the subject reports having an RCE at a center not participating in the study, every effort should be made to obtain medical records from the center. An overview of the activities and data to be collected is provided below.

- Review subject medical records since the date of the baseline visit and assess for RCEs and reportable AEs
- If RCEs are identified during the medical record review (see Figure 3 for details), complete the “Reviewable Clinical Event” eCRF.
  - Each newly identified RCE must have a unique eCRF. For example, if the subject had two HF outpatient visits for an on-going AE it must be captured in two separate “Reviewable Clinical Event” eCRFs.
  - If a single RCE is associated with multiple AEs, only the primary AE (i.e., the chief complaint leading to the clinic/hospital visit) should be associated with an “Reviewable Clinical Event” eCRF. For example, if a subject was admitted due to symptoms of gastrointestinal bleeding but developed worsening HF during the course of hospitalization, the gastrointestinal bleeding would be the primary AE, and therefore it would be associated with the “Reviewable Clinical Event” eCRF. A separate “Reviewable Clinical Event” eCRF is not required for the in-patient worsening of HF even if it is reported as a separate AE.
- For hospitalizations, the Principal Investigator must review the patient’s medical records and classify the primary organ cause in the “Reviewable Clinical Event” eCRF (see Appendix for details). Appropriate classification is important for event subgroup analysis. Classification also triggers the request for medical record documentation to be sent to BSC.

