### **9.9 Final Clinic Visit [350-430 days]**

The final visit must be performed in-clinic 350 to 430 days following the baseline visit. If the patient is withdrawn prior to the window for the final clinic visit, please complete the final clinic visit at the point of withdrawal. An overview of the data to be collected at this visit is provided below.

- Review subject medical records since the date of the baseline visit and assess for RCEs and reportable adverse events.
  - Collect and report using the same process used in the interim medical record review (See section 9.8).
- Physical assessment (See Appendix)
- Blood labs: Enter the most recent blood lab values since the baseline visit for the following.
  - Natriuretic peptides (BNP or NT-proBNP) and date of collection. If serial natriuretic peptide data has already been entered in the supplementary diagnostics form, the same values need not be entered in the final visit eCRF.
  - Creatinine and date of collection
- Supplementary diagnostics data collection:
  - Collect using the same process as in the interim medical record review (See section 9.8).
- Interrogate the device with a PRM. This ensures that the device data will be uploaded when the patient returns to within range of the communicator.
- Confirm that a LATITUDE transmission occurred in the previous 90 days. If transmission has not occurred instruct patient to do a patient initiated interrogation when they are in range of their communicator.
- Remote monitoring usage:
  - Provide information about the frequency and use of remote monitoring to manage the patient's HF condition over the past 12 months (e.g. sleep incline, weight, blood pressure, arrhythmia burden).

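### No check of LATITUDE transmission is required between baseline and the final visit, so a subject with no upload after baseline can lose up to 65 early days of sensor data

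*Protocol*

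**What the plan says.** **Route of the data.** Section 9.2 states: "HF Sensor data and Sleep Incline data will be collected via the LATITUDE patient communicator". Section 4.2 calls LATITUDE the primary means of device data collection.

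**Device memory.** Section 4.2: "Sensor data will be stored in the PG for 365 days after which the earliest data are overwritten".

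**Upload schedule.** Section 4.2: "To ensure timely data transmission, LATITUDE must be programmed for scheduled follow-ups to occur every 3 months or sooner". Sections 8.4 and 9.7 repeat the setting, which is confirmed at baseline.

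**Required checks.** Section 4.2 says that transmission "must be confirmed at the baseline visit". In Table 9-1 the row "Confirmation LATITUDE Transmission" is mandatory at baseline and at the final visit, and blank (a dash) at the interim review. Section 9.8 says: "The interim medical record review must be conducted 150 to 210 days following the baseline visit". Its task list covers clinical events, adverse events and supplementary diagnostics, and names nothing on LATITUDE. For the final visit, day 350 to 430, section 9.9 says: "Confirm that a LATITUDE transmission occurred in the previous 90 days". If there was none, the subject is told to start an interrogation when in range of the communicator.

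**Exit.** Section 6 (text under Figure 4) has the end-of-study form completed once the site has confirmed the transfer of device data.

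**Use of the data.** Section 10.1.2 counts an index HF hospitalization as usable only if sensor data are available during the event. It plans for 215 usable events and allows a 20% loss for events too close to study start or exit.

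**The concern.** The first required look at transmission after baseline can come later than the device memory reaches back. A communicator confirmed as working on day 0 may stop sending, and nobody is obliged to look until day 350 to 430. At a day-430 visit the device holds only days 65 to 430. The days before that cannot be recovered by any later interrogation.

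The three-monthly schedule is a setting. It does not show that uploads arrive: section 4.2 itself notes that no upload occurs while the subject is out of range, and section 9.9 asks for evidence of a recent transmission. Access to the server (section 4.2) and general monitoring (section 15) make a missed upload visible, but no passage requires anyone to act on one.

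At stake are sensor data for the primary objective. An index hospitalization in the overwritten days cannot be used. The 20% allowance is described only in terms of closeness to study start and exit and does not name failed transmission. The planned power has little room: the calculation below gives 80.6% against a target of at least 80%.

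**Working it through.** **Inputs from the protocol.** Memory 365 days and uploads at least every 3 months (4.2); interim review day 150-210 (9.8); final visit day 350-430 (Table 6-1, 9.9); 215 usable index events, 20% with readmission, 3:1 ratio, standardized difference 0.5, two-sided alpha 0.05 (10.1.2).

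**Input not given.** The share of subjects with no upload after baseline. It is assumed below, from 1% to 20%.

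**1. The plan's own figures**
- Readmission group: 0.20 x 215 = 43. Comparison group at 3:1: 129. The remaining 215 - 172 = 43 cover the excluded 31-60-day readmissions.
- Two-sample t-test, noncentral t, noncentrality 0.5 / sqrt(1/43 + 1/129) = 2.84 on 170 degrees of freedom: power 80.6%. With 42 and 126: 79.7%. The figure of 215 is reproduced.
- 215 / 0.8 = 269 (270 stated); 270 / (0.09 x 0.8) = 3750.

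**2. Days lost to overwriting**

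Let t be the day of the last successful upload and D the day of the upload that recovers the data, both counted from baseline. Then days lost = max(0, D - 365 - t).

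| Last upload t | D = 350 | D = 390 | D = 430 | No loss until day |
|---|---|---|---|---|
| 0 (baseline only) | 0 | 25 | 65 | 365 |
| 30 | 0 | 0 | 35 | 395 |
| 60 | 0 | 0 | 5 | 425 |
| 65 | 0 | 0 | 0 | 430 |
| 90 | 0 | 0 | 0 | 455 |

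Loss by day 430 thus needs two things: no successful upload after about day 65, and a recovering upload after day 365. Each day between the final visit and the actual upload adds one day of loss.

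If final visits are spread evenly over days 350-430 (assumption), 65/80 = 81% fall after day 365. The mean loss for a subject with t = 0 is then 0.81 x 32.5 = about 26 days.

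**3. Effect on usable events and power**

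Let f be the assumed share of subjects with no upload after baseline. The share of follow-up lost is f x (days lost / D). Usable events = 215 x (1 - share), with both groups reduced in proportion.

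| f | Final visits | Share lost | Usable events | Power |
|---|---|---|---|---|
| 1% | all on day 430 | 0.01 x 65/430 = 0.15% | 214.7 | 80.6% |
| 5% | all on day 430 | 0.05 x 65/430 = 0.76% | 213.4 | 80.3% |
| 10% | all on day 430 | 0.10 x 65/430 = 1.51% | 211.8 | 80.0% |
| 20% | all on day 430 | 0.20 x 65/430 = 3.02% | 208.5 | 79.4% |
| 5% | spread evenly, mean day 390 | 0.05 x 26.4/390 = 0.34% | 214.3 | 80.5% |
| 10% | spread evenly, mean day 390 | 0.10 x 26.4/390 = 0.68% | 213.5 | 80.3% |

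**4. With a check at the interim review**

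At day 210 all 210 days since baseline are still in memory. An upload then protects the record until day 210 + 365 = 575; one at day 150, until day 515. Both lie beyond the last permitted visit.

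**The case against.** The strongest reply is that the exposed case is narrow. A communicator shown to work at baseline must fail before its first effective upload and stay failed for about a year. A single quarterly upload near day 90 protects everything until day 455, and a final visit by day 365 loses nothing even with no upload since baseline. All of this stands.

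Nor do the documents show that a failure would go unnoticed. The study doctor and the sponsor can see the LATITUDE server throughout, and remote and central monitoring is planned. That also stands, but it describes the ability to see, not a duty to look or act. Since Table 9-1 asks for no interim confirmation, a mid-study silence breaches no scheduled check.

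Rescue at exit is better than it may look, because completion of the end-of-study form follows confirmed transfer. That limits total loss, but it cannot restore days already overwritten. The 20% allowance may also cover part of the same loss, since the overwritten days are those nearest to study start. The estimates above take no credit for this.

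Finally, following up missed transmissions can be left to a monitoring plan. That is fair, and it is one reason to rate the point as minor.

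**Conclusion.** The gap is real and its effect is small. Between baseline and day 350-430 the protocol requires neither a check of transmission nor action on a missed upload. A subject with no upload after baseline can irreversibly lose up to 65 early days by a day-430 visit, or more if the last upload is delayed.

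At assumed failure rates of 5-10% with every final visit on day 430, overwriting costs about 2 to 3 of 215 usable events, and power goes from 80.6% to about 80.3-80.0%. It falls just below 80% at an assumed 20% (79.4%).

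A reader might infer a larger loss: if 5-10% of subjects yielded no sensor data at all, 215 would fall to about 204-194 and power to 78.6-76.3%. The documents do not support that as the effect of overwriting. It removes every event in the affected subjects and supposes that they are never recovered, although the protocol makes exit follow confirmed transfer. A reader might also infer that any communicator failure destroys the first weeks of data. It does so only when nothing was uploaded after about day 65.

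**What to change.** In Table 9-1, change the interim review cell of the row "Confirmation LATITUDE Transmission" from a dash to X. In section 9.8, add the check that section 9.9 already contains: confirm on LATITUDE that a transmission took place in the last 90 days and, if not, have the subject start an interrogation in range of the communicator and correct the communicator problem.

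The check fits into a record review that already takes place and needs no clinic visit. It costs one website check per subject and a call to those who are not transmitting.

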## 5 Study Objectives and Endpoints

The PREEMPT-HF study is designed to collect device and clinical event data to evaluate extended applications of HeartLogic in a broad sample of HF subjects with an implantable ICD or CRT-D.

### 5.1 Primary Objective

The primary objective of the PREEMPT-HF study is to investigate the association between HF Sensor data and 30-day HF readmissions.

Subjects will be followed for approximately 12 months to collect the required number of clinical events to support the study objectives. These events are called Reviewable Clinical Events (RCEs), and include all-cause hospitalizations and HF outpatient visits (as defined below).

[figure not shown]
RCEs require the investigational site to review the subject's medical records and complete the appropriate eCRF (Figure 3).

Clinical events for the purposes of data analysis are defined as follows:

- **Hospitalization (all-cause):** the subject is admitted to inpatient hospital care and discharged on a different calendar date.
- **HF Hospitalization:** the subject is admitted with signs/symptoms of congestive heart failure (CHF) and receives unscheduled augmented HF therapy with oral or intravenous medications, ultrafiltration therapy or other parenteral therapy.
- **HF Readmission (30-day):** the subject is admitted for an unplanned hospitalization for any cause within 30 days post discharge from a HF hospitalization.
- **HF Outpatient Visit:** the subject has signs/symptoms of congestive HF, and receives unscheduled intravenous decongestive therapy (e.g., IV diuretics, IV inotropes, IV vasoactive drugs, ultrafiltration), in a setting that does not involve a hospitalization (e.g.: emergency room, HF clinic, primary care clinic, etc.).

**Figure 3: Reviewable Clinical Events Data Requirements in relation to AE reporting**

## **5.2 Additional Objectives**

Additional objectives of the PREEMPT-HF study are intended to:

1. Characterize HF Sensor data for:
  - Association with risk for device VT/VF therapy
  - Phenomapping of HF events
  - Association with non-HF hospitalizations including cardiac non-HF events and non-cardiac events
2. Collect subject Sleep Incline Sensor data prior to and following reviewable clinical events
3. Link study data to third-party data, such as Center for Medicare and Medicaid Services (CMS) administrative claims (US only). Association of reviewable clinical study events with other sources will be investigated. Any study data linkage will abide by all applicable laws, regulations, and data use agreements, and patients will be consented accordingly.

## **5.3 Study Endpoints**

PREEMPT-HF is a non-mandated post-market study. Data will be collected in subjects treated per usual standard of care procedures. However, the device needs to be programmed with Heart Failure Sensors ON and HeartLogic disabled. There are no pre-defined endpoints, and there are no special clinical evaluations or tests that are not a part of standard of care.

## **6 Study Design**

[figure not shown]
PREEMPT-HF study is a global, multi-center, prospective, non-randomized study. The study objective is to evaluate extended applications of HF sensor measurements in relation to RCEs (i.e., all-cause hospitalizations and HF outpatient visits). Device data will be collected using the LATITUDE remote monitoring system. However, it is critical to report RCEs via the eCRFs as defined in the study protocol.

Prior to enrollment, patients who meet the eligibility criteria (Sections 7.2 and 7.3) and agree to participate in the study will be asked to sign a Subject Informed Consent document approved by an Institutional Review Board/Ethics Committee, or Competent Authority (as applicable per local regulations). The follow-up schedule for subjects is shown in Table 6-1, and the overall study flow is shown in Figure 4.

**Table 6-1: Visit and Review Schedule**

Visit	Window
Enrollment Visit	The subject may be enrolled at any time following device implant
Baseline Visit	The baseline visit must be conducted at least 7 days following implant, and within 30 days of subject consent
Interim Medical Record Review (6 month)	150 to 210 days from baseline visit
Final Clinic Visit (12 month)	350 to 430 days from baseline visit (or at the point of withdrawal)

**Figure 4: PREEMPT-HF Study Design**

All subjects will be evaluated at the baseline visit and will be followed until the final in-clinic visit (approximately 12 months). Study visits should be scheduled, if possible, to coincide with standard of care visits. At the baseline visit the subject should be provided with a study ID card containing contact numbers for site research staff. The subject should be informed to contact site research staff if hospitalized or treated with IV HF therapy, including events that occur at a non-study hospital or physician’s office.

An interim medical record review is required at 6 months to capture study clinical events (see section 6). No subject visit is required. Accurate and comprehensive capture of RCEs is critical for the success of the study. When possible, this medical record review should coincide with an in-clinic standard of care visit so that the investigator can ask the subject about any RCEs that may have occurred since the last visit.

During the final clinic visit (12 months or at the point of withdrawal), a device interrogation using the PRM must be performed. This ensures that the device data will be uploaded the next time the subject is in contact with their LATITUDE system at home. Once the site has confirmed device data transfer via LATITUDE, the end of study eCRF must be completed. There will be no further data collection for that subject. Individual subjects are then exited from the study, and the Heart Failure Sensors and feature can be programmed per clinician discretion.

### ***6.1 Scale and Duration***

Up to 3750 subjects will be enrolled in United States, Canada, Europe, and Asia Pacific. Sites may continue to enroll subjects until notified of enrollment completion. The maximum enrollment ceiling per site is 375 subjects. Enrollments are expected to occur over a period of approximately 60 months. Subjects enrolled in the study will be followed for approximately 12 months. A patient can be in the study for up to 460 days (15 months) if the maximum visit windows are taken in to account. The study will be conducted at up to 200 sites globally and the study is expected to be completed in approximately 6 years.

### ***6.2 Treatment Assignment***

There is no treatment assignment in this study.

### ***6.3 Treatment and Control***

This is an observational study with no treatment or control groups. All enrolled subjects will already be implanted with a commercially available Boston Scientific CRT-D or ICD device. For the specific model numbers see Table 4-1. Devices will have Heart Failure Sensors turned ON, Respiratory Sensor turned ON, Sleep Incline Sensor turned ON, and HeartLogic disabled.

### ***6.4 Justification for the Study Design***

The results of the MultiSENSE study were based upon 400 subjects followed for 12 months (test cohort). While this provided sufficient sample size to evaluate HeartLogic performance to predict the initial (index) HF event, it was not sufficient for analyzing HF readmissions. Thus, a much larger sample size is needed to obtain sufficient numbers of subjects with HF readmissions. To evaluate HeartLogic for HF readmissions, subjects cannot be treated by using the feature, and clinicians must be blinded to HeartLogic Index and alerts. Therefore, this study will only enroll subjects who have HeartLogic disabled. Data from this study will be used to evaluate the association of HF sensor measurements with 30-day HF readmissions.

